6.3.2. Smoking Status

Baseline smoking status (never, former, and current) for the randomized withdrawal treatment period is determined from the baseline smoking status of the open-label treatment period and tobacco use during the randomized withdrawal treatment period. A ‘current’ smoker becomes a ‘former’ smoker if the subject indicates a change in tobacco use at the start of the open-label treatment period and does not consume any tobacco products during the open-label treatment period. Conversely, a ‘never’ or ‘former’ smoker becomes a ‘current’ smoker if the subject indicates a change in tobacco use and reports consuming a tobacco product at any visit of the open-label treatment period.

6.4. Variables

6.4.1. Study Day

If the date of interest occurs on or after the date of first dose (first dose of the open-label treatment period), Study Day will be calculated as (date of interest – date of first dose) + 1.

If the date of interest occurs before the date of first dose, Study Day will be calculated as (date of interest – date of first dose).

The analysis dataset variable “Analysis Study Day” is defined in the Visit Windows Section (6.4.5).

6.4.2. Age

Only year of birth is captured in the clinical database. Hence, for analysis purposes, each subject’s age at enrollment into Study 0170 will be their age in integer years as reported by the site.

6.4.3. Change from Baseline

Change from baseline is calculated as postbaseline result – baseline result. If either the baseline or the postbaseline result is missing, change values are treated as missing.

6.4.4. BMI (Body Mass Index)

BMI is calculated as:

$$BMI (kg / m^2) = \frac{weight (kg)}{height (m)^2}.$$

6.4.5. OHSA#1

For each of the 6 questions in the Orthostatic Hypotension Symptom Assessment (Section 8.8.1), respondents are asked to rate the average severity of their symptoms over the past week on an ordinal scale from 0 to 10. The text of question 1 is shown below:

OHSA#1. Dizziness, lightheadedness, feeling faint, or feeling like you might black out												
NONE	0	1	2	3	4	5	6	7	8	9	10	WORST POSSIBLE

Subjects who complete the Week 4 visit during the open-label treatment period must have shown a Week 4 OHSA#1 decrease of at least 2 points to be eligible to continue open-label ampreloxetine treatment. For Study 0169 completers, this means a decrease from their Study 0169 baseline rating; for De Novo subjects, a decrease from their V1 rating. Subjects who complete the Week 16 visit at the end of the open-label treatment period must have a Week 16 (V6, D113) OHSA#1 rating of 7 or lower to be eligible to begin the randomized withdrawal treatment period.

Worsening in OHSA#1 During the Randomized Withdrawal Treatment Period

Worsening in OHSA#1 will be defined only for subjects with a baseline score < 10, as an increase from the baseline score. (Per protocol, all subjects should have a baseline score ≤ 7.) Worsening rates at postbaseline visits will be summarized in 2 ways: 1) including only subjects for whom a score was recorded, and 2) counting subjects for whom no score was recorded as having worsened.

6.4.6. Patient's Global Impression of Severity (PGI-S)

PGI-S is an ordinal scale which asks respondents to select the choice that best describes the current severity of symptoms of their neurogenic orthostatic hypotension. The recall period is the past week. Two versions were used in this study: a 7-point version initially and later a 5-point version. For analyses, any PGI-S scores recorded using the 7-point scale will be mapped to the 5-point scale as shown in Table 2.

Table 2: PGI-S Mapping From 7-Point to 5-Point Scale

7-Point Scale	5-Point Scale
Normal, not at all ill (1)	None (1)
Borderline ill (2)	Mild (2)
Mildly ill (3)	
Moderately ill (4)	Moderate (3)
Markedly ill (5)	Severe (4)
Severely ill (6)	
Extremely ill (7)	Very severe (5)

Listings will show the 5-point scale responses for all subjects and the 7-point scale responses for subjects who used that scale.

Worsening in PGI-S During the Randomized Withdrawal Treatment Period

Worsening in PGI-S will be defined only for subjects with a baseline score < 5, as an increase from the baseline score. Worsening rates at postbaseline visits will be summarized in 2 ways: 1) including only subjects for whom a score was recorded, and 2) counting subjects for whom no score was recorded as having worsened. Both types of summaries will exclude subjects with a baseline score of 5.

6.4.7. Treatment Failure

Treatment failure is defined as meeting the following criteria at Week 6 following randomization:

Change (worsening) from baseline in OHSA#1 score of at least 1 point and worsening of disease severity as indicated by at least a 1-point change from baseline in PGI-S

The assessments done at the Week 16 visit in the open-label treatment period prior to randomization are considered baseline for the randomized withdrawal treatment period. Subjects who withdraw for any reason prior to Week 22 or fail to provide assessments at Week 22 will be counted as treatment failures, including subjects whose randomized withdrawal treatment period study disposition is reported as "Study Terminated by Sponsor." Subjects with a baseline score for either OHSA#1 or PGI-S which cannot worsen (e.g., a baseline PGI-S score of 5) will be counted as treatment failures if the other score is worse at Week 22 (or was not obtained).

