8.2. Sample Size and Power

Assuming that 60% are eligible for randomization at the end of the 16-week OL period, approximately 258 subjects will be enrolled such that 154 subjects are expected to continue into the randomized treatment period. For the De Novo Group, the goal is to enroll at least 40% of MSA subjects.

The primary analysis will occur when all subjects in the Full analysis set (FAS) (Section 8.3.2) of double-blinded randomized withdrawal phase of the study have either completed the primary endpoint assessment (OHSA#1 and PGI-S at Week 6 post randomization) (V9, D155) or discontinued earlier and the database has been cleaned and locked. A sample size of 154 at randomization will provide an overall power of 90% to detect a difference of 25% (25% TD-9855 vs. 50% PBO) in the primary endpoint of proportion of subjects that meet the criteria of treatment failure at Week 6 (V9, D155) during the double-blind randomized withdrawal phase at two-sided alpha level of 0.05.

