8.5.1.1. Primary Efficacy Evaluation

The primary study endpoint is the proportion of treatment failure at Week 6 during the double-blind randomized withdrawal phase. Treatment failure is defined as subjects who meet the following criteria at Week 6 following randomization:

Change (worsening) from baseline in OHSA#1 score of 1.0 point and worsening of disease severity as assessed by a 1-point change in PGI-S.

The assessments done at the Week 16 (V6, D113) visit in the OL phase prior to randomization are considered baseline for the double-blind randomized withdrawal phase of the study. Subjects who withdraw for any reason prior to V9 (D155) or subjects who fail to provide assessment at V9 (D155) will be considered as treatment failures.

Logistic regression model will be used to compare treatment differences based on the FAS. The model will include fixed effect class terms of treatment, baseline disease type (MSA, PAF, PD), and continuous covariate of baseline OHSA#1 score, and baseline PGI-S score. Odds Ratio with 95% confidence intervals will be calculated and presented, least-square proportion and 95% confidence intervals on the differences between TD-9855 and placebo groups will be calculated and presented. In addition, the proportion of subject with treatment failure along with proportion of subjects failing separately due to worsening of OHSA#1 and PGI-S will be reported.

Sensitivity analyses on the primary endpoint will be carried out (1) using per-protocol set which excludes subjects with major protocol deviations, (2) using multiple imputation for subject missing OHSA#1 and/or PGI-S score at Week 6 post randomization (V9, D155) and (3) by excluding subjects with missing data on primary endpoint. Additional sensitivity analyses may be defined in the SAP.

The primary analysis will be repeated on a set of pre-specified subgroups (e.g., disease type) and presented in graphical format. Details will be specified in the Statistical Analysis Plan (SAP).

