3.2. Study Endpoints

3.2.1. Primary Study Endpoint

The primary study efficacy endpoint is the proportion of treatment failure at Week 6 during the double-blind randomized withdrawal treatment period. Treatment failure is defined as subjects who meet the following criteria at Week 6 following randomization (V9, D155):

Change (worsening) from baseline in OHSA#1 score of at least 1.0 point and worsening of disease severity as assessed by at least 1 point change in PGI-S

The assessments done at the Week 16 (V6, D113) visit in the open-label treatment period prior to randomization are considered baseline for the double-blind randomized withdrawal treatment period of the study. Subjects who withdraw for any reason prior to V9 (D155) or subjects who fail to provide the required assessments at V9 (D155) will be considered as treatment failures.

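### The primary endpoint rule does not state how a subject with only one of OHSA#1 and PGI-S at V9 is coded, and its plainest reading makes failures of some who cannot meet the two-score criterion

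*SAP*

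**What the plan says.** SAP 6.4.7 defines failure as a conjunction: "Change (worsening) from baseline in OHSA#1 score of at least 1 point and worsening of disease severity as indicated by at least a 1-point" deterioration on PGI-S. It then says "Subjects who withdraw for any reason prior to Week 22 or fail to provide assessments at Week 22 will be counted as treatment failures". SAP 3.2.1 gives the parallel rule: "subjects who fail to provide the required assessments at V9 (D155) will be considered as treatment failures". Protocol 8.2 shows what counts as complete, since it times the primary analysis by when subjects have "completed the primary endpoint assessment (OHSA#1 and PGI-S at Week 6 post randomization", or have left the study.

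Two other places bear on a single missing score:

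- SAP 6.4.7 adds a ceiling rule. Subjects whose baseline on one score leaves no room to worsen (PGI-S of 5 is the example) "will be counted as treatment failures if the other score is worse at Week 22 (or was not obtained".
- SAP 6.4.5 and 6.4.6 summarise worsening on each score separately, in two ways. The second does so by "counting subjects for whom no score was recorded as having worsened".

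Protocol 8.5.1.1 foresees that one score may be missing without the other: a sensitivity analysis is planned "using multiple imputation for subject missing OHSA#1 and/or PGI-S score at Week 6 post randomization". SAP 8.4.1 lists a per-protocol repeat and a repeat excluding subjects who missed Week 6 because the sponsor ended the study. It does not list the imputation analysis.

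**The concern.** Under an AND rule, one recorded score can settle the outcome. If OHSA#1 is recorded at V9 and has not worsened, although it had room to, the subject cannot meet the symptom criterion whatever PGI-S would have been. The same holds with the scores exchanged. Coding that subject as a failure is not a cautious guess about an unknown outcome, because the two-score criterion is already known not to be met.

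Two things are at stake. The first is the coding itself: recoded non-failures bring the arms closer together if the gaps are equally frequent, and distort the comparison if they are not. The second is reproducibility. The primary endpoint should have one derivation, and the SAP text supports two.

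**Working it through.** **The one-score cases under each reading.** Under the either-missing reading, any absent score makes the subject a failure. Under the component-wise reading, a missing score counts as worsened on that score only, and the AND rule and ceiling rule are then applied.

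| Subject at V9 | Either-missing | Component-wise |
|---|---|---|
| A. One score recorded, had room to worsen, did not; other missing | Failure | Non-failure |
| B. One score recorded and worse; other missing | Failure | Failure |
| C. Baseline PGI-S 5, PGI-S missing, OHSA#1 recorded and not worse | Failure | Non-failure |
| D. Baseline PGI-S 5, PGI-S recorded, OHSA#1 missing | Failure | Failure (ceiling rule) |
| E. Withdrew, or neither score | Failure | Failure |

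Only A and C differ. C also shows a conflict inside SAP 6.4.7: the general sentence, read as either-missing, gives failure. The ceiling sentence asks for the other score to be worse or absent, and here it is present and not worse.

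**The plan's own figure.** Inputs from Protocol 8.2: failure 25% on TD-9855 and 50% on placebo, two-sided alpha 0.05, power 90%; allocation is 1:1 (Protocol 5.1). With pooled variance under the null and no continuity correction:

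n per arm = [1.96 × √(2 × 0.375 × 0.625) + 1.2816 × √(0.25 × 0.75 + 0.50 × 0.50)]² / 0.25² = (1.342 + 0.848)² / 0.0625 ≈ 76.7, so 77 per arm and 154 in all.

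Power at 77 per arm is 90.1%. The stated 154 and 90% are reproduced, and the point does not touch them.

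**Illustrative size.** Let m be the share of true non-failures recoded as failures. The documents give no value, so m is an assumption. The observed failure rate becomes p′ = p + m(1 − p). With equal m in both arms the difference shrinks to 25 × (1 − m) points. Extra failures per arm are 77 × m × 0.75 on TD-9855 and 77 × m × 0.50 on placebo.

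| m (both arms) | TD-9855 | Placebo | Difference (points) | Extra failures (TD-9855 / placebo) | Power at 77 per arm |
|---|---|---|---|---|---|
| 0 | 25.0% | 50.0% | 25.0 | 0 / 0 | 90.1% |
| 1% | 25.8% | 50.5% | 24.75 | 0.6 / 0.4 | 89.3% |
| 2% | 26.5% | 51.0% | 24.5 | 1.2 / 0.8 | 88.5% |
| 5% | 28.8% | 52.5% | 23.75 | 2.9 / 1.9 | 85.8% |
| 10% | 32.5% | 55.0% | 22.5 | 5.8 / 3.9 | 81.0% |

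With unequal m, 5% on TD-9855 only gives power of 77.5%, and 5% on placebo only gives 94.6%. With no true effect and 5% on placebo only, the two-sided rejection rate is 6.1% if the true failure rate is 50%, and 8.2% if it is 25%, instead of 5%. One subject moves an arm by 1/77 = 1.3 points.

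**The case against.** A reader might infer that the SAP lays down a rule under which known non-failures are counted as failures. The documents do not go that far. No sentence addresses a subject with one score missing and the other recorded and not worse. The closing words of the ceiling sentence would be redundant if any single gap already meant failure, and the component summaries treat a missing score as worsening on that score alone. Both fit a reading under which this subject is already a non-failure. That stands, and it is why the point is partly one of ambiguity. It does not remove the point, because the reference to required assessments, taken with Protocol 8.2, still reads most naturally as requiring both scores.

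A reader might also take the power losses as real. They assume that 25% and 50% are rates before any recoding. The protocol's endpoint already counts missing V9 assessments as failures, so the planning rates may include them, and adding m would then count the effect twice. The likely frequency is also low: Protocol 6.3.10 puts the OHQ and PGI-S next to each other among the procedures to be done first at V9. Both objections to size stand.

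Counting absence as failure is also part of the declared endpoint. For withdrawals and subjects with neither score that is a legitimate composite choice, and those subjects are not known non-failures. For the one-score subject the choice is not clearly declared.

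Finally, if the protocol's imputation analysis fills in the separate scores and then applies the AND rule, case A is a non-failure in every imputed dataset. But SAP 8.4.1 does not carry that analysis, and SAP 11.2 does not list it as dropped. The by-subject listing in SAP 8.4.1 would make such cases visible, but no listed analysis recodes them.

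**Conclusion.** The point holds in a limited form. On the plainest reading of SAP 3.2.1 and 6.4.7 with Protocol 8.2, a V9 attendee with one recorded score that could have worsened and did not is a failure, although the two-score criterion cannot be met. Because SAP 6.4.5 to 6.4.7 also support the opposite coding, the derivation of the primary endpoint is ambiguous.

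Only subjects with exactly one score at V9 are affected. Their number is not given and is probably very small. Equal frequency in the two arms would dilute the effect slightly; unequal frequency could bias it in either direction, so the rule cannot be called reliably conservative. The power figures are illustrations resting on an assumed m and on planning rates free of recoding. They are not estimates of a loss in this trial.

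**What to change.** Add to SAP 3.2.1 and 6.4.7, with a matching clarification in the protocol:

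*A subject who completes V9 with exactly one of the two scores recorded is a non-failure if the recorded score could have worsened from baseline and did not worsen by at least 1 point, and a failure otherwise; the rule for baseline scores that cannot worsen still applies. Subjects who withdraw before V9 or provide neither score are failures.*

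The reference to the ceiling rule is needed so that a subject with baseline PGI-S 5 and no OHSA#1 at V9 remains a failure, as SAP 6.4.7 now says. Report the number of one-score subjects by arm.

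The cost is two sentences in the SAP, the protocol clarification, a small change in the derivation code and one line in a table. No new data are needed, and outcomes that are truly unknown remain failures.

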3.4. Study Endpoints

3.4.1. Primary Endpoint

The primary study endpoint is the proportion of treatment failure at Week 6 during the double-blind randomized withdrawal phase. Treatment failure is defined as subjects who meet the following criteria at Week 6 following randomization (V9, D155):

Change (worsening) from baseline in OHSA#1 score of 1.0 point and worsening of disease severity as assessed by a 1-point change in PGI-S.

The assessments done at the Week 16 (V6, D113) visit in the OL phase prior to randomization are considered baseline for the double-blind randomized withdrawal phase of the study. Subjects who withdraw for any reason prior to V9 (D155) or subjects who fail to provide assessment at V9 (D155) will be considered as treatment failures.

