11.2. Changes to Protocol-Specified Analyses

- Removal of smoking status subgroups
- Addition of baseline norepinephrine subgroups
- To the planned analyses of standing SBP at 3 minutes and at 10 minutes during the orthostatic standing test, addition of similar analyses of standing heart rate at 3 minutes and at 10 minutes

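### The ceiling rule in SAP 6.4.7 fails a subject with baseline PGI-S 5 whose OHSA#1 rises by at least 1 point, even when PGI-S has improved at Week 22

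*SAP*

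**What the plan says.** Protocol 3.4.1 defines treatment failure at Week 6 after randomization (V9, Week 22) by two conditions joined by 'and': "Change (worsening) from baseline in OHSA#1 score of 1.0 point and worsening of disease severity as assessed by a 1-point change in PGI-S". SAP 3.2.1 repeats this with thresholds of at least one point: "Change (worsening) from baseline in OHSA#1 score of at least 1.0 point and worsening of disease severity as assessed by at least 1 point change". SAP 6.4.7 says the same. The only exception in the protocol is for subjects who withdraw or give no V9 assessment; they are failures.

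The last sentence of SAP 6.4.7 adds a ceiling rule that the protocol does not have. It concerns "Subjects with a baseline score for either OHSA#1 or PGI-S which cannot worsen (e.g., a baseline PGI-S score of 5" and says that they "will be counted as treatment failures if the other score is worse at Week 22 (or was not obtained".

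Two other SAP statements bear on the same subjects. Section 6.4.6 states: "Worsening in PGI-S will be defined only for subjects with a baseline score < 5, as an increase from the baseline score". It says of the PGI-S worsening summaries: "Both types of summaries will exclude subjects with a baseline score of 5". SAP 11.2 lists three changes to protocol-specified analyses, one being "Addition of baseline norepinephrine subgroups". The ceiling rule is not among them.

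**The concern.** The ceiling rule tests one score only, the one that was not at its maximum at baseline. It sets no condition on the Week 22 value of the score that was. A score at its maximum can stay or improve, and the rule treats the two outcomes alike. Where it improved, the subject is scored as failing an endpoint that requires worsening on both scales while moving the other way on one of them.

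Such a baseline is possible. Randomization criterion 201 caps OHSA#1 at 7, and no criterion names PGI-S. The SAP anticipates the case, since it uses baseline PGI-S 5 as its example. The OHSA#1 branch should not arise, because of the cap.

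The same subject would then be a failure on the primary endpoint, an improvement on change in PGI-S (fourth in the testing sequence of SAP 8.6), absent from the PGI-S worsening summaries, and without a defined PGI-S status for the Week 6 concordance table in SAP 8.4.1.

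**Working it through.** **1. The rule, outcome by outcome.** Take baseline PGI-S 5, OHSA#1 up by at least 1 point, and both scores obtained at Week 22.

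| Week 22 PGI-S | Movement | Strict two-scale definition | SAP 6.4.7 as written | With the condition 'still at maximum' |
|---|---|---|---|---|
| 5 | unchanged | not a failure | failure | failure |
| 4, 3, 2 or 1 | improved | not a failure | failure | not a failure |

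If OHSA#1 is unchanged or better and both scores are obtained, all three rules agree on non-failure. The disputed cases are the four improved outcomes in the second row. No other section of the SAP or protocol restricts them.

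**2. The plan's own power figure.** Inputs from Protocol 8.2: 154 randomized; 25% against 50% failure; two-sided alpha 0.05. The 1:1 allocation gives 77 per arm. With pooled variance and no continuity correction:

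- mean rate = (0.25 + 0.50)/2 = 0.375
- null term = 1.960 × √(2 × 0.375 × 0.625) = 1.342
- alternative SD term = √(0.25 × 0.75 + 0.50 × 0.50) = 0.661
- power = Φ[(0.25 × √77 − 1.342)/0.661] = Φ(1.288) = 90.1%

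The stated 90% is reproduced.

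**3. How many subjects.** The documents give no share with baseline PGI-S 5. Assume 2% to 10%: 0.02 × 154 = 3.1 and 0.10 × 154 = 15.4 subjects.

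For the chance that such a subject is affected, assume bivariate normal changes rounded to integers: SD 2 for OHSA#1, SD 0.9 for PGI-S, correlation 0.3 to 0.6. OHSA#1 is worse if its unrounded change is at least 0.5. PGI-S has improved if its unrounded change is below −0.5.

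- No mean drift on either scale: P(OHSA#1 worse) = 1 − Φ(0.25) = 0.40. P(PGI-S improved given that) = 0.19 at correlation 0.3 and 0.09 at 0.6. Joint: 0.077 and 0.038.
- Mean drift of 1 on OHSA#1 and 0.5 on PGI-S: P(OHSA#1 worse) = Φ(0.25) = 0.60. Conditional probability 0.09 and 0.04. Joint: 0.054 and 0.026.

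The range is 0.026 × 3.1 = 0.1 subject to 0.077 × 15.4 = 1.2 subjects. A drift of 1 on OHSA#1 with none on PGI-S would raise the joint probability to 0.132 at most, or 0.132 × 15.4 = 2.0 subjects. That combination is less plausible, because the two ratings would be expected to move together.

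**4. What that could do.** One subject is 1/77 = 1.3 percentage points of an arm. Take 25% and 50% as the rates under the repaired rule and let the rule as written add 1% (0.8 subject) to each arm. The formula in step 2 with 26% and 51% gives 89.8%, against 90.1%. If the 1% fell only in the TD-9855 arm, power would be 87.4%; only in the placebo arm, 92.1%. The one-arm cases are bounds, since the rule's wording does not single out an arm.

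**The case against.** The strongest objection is that any ceiling rule departs from the two-scale wording. Under the strict definition a baseline-5 subject with both scores obtained can never fail, so the SAP reasonably falls back on the scale that can still worsen. That stands for subjects who stay at 5, and it is why the repair keeps them as failures. It does not cover subjects whose PGI-S improved: for them the second scale is informative and points the other way.

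Four stronger readings might be inferred, and the documents do not support them.

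- *The affected failures cannot be traced.* The summary tables do not show them. However, SAP 8.4.1 provides a listing of all FAS subjects with both baseline scores, both Week 22 changes and failure status, and each such subject would be visible there.
- *These failures have nothing to do with relapse.* The rule requires OHSA#1 to be worse, and Protocol 3.2 treats OHSA#1 as the validated efficacy measure in this population. The accurate statement is that the two ratings disagree, so the two-scale definition is not met.
- *The rule favours one arm.* It is triggered by a baseline value and applies to both blinded arms. The direction of any net effect is unknown.
- *Counting an unobtained score as failure is part of the error.* It agrees with the general missing-assessment rule.

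It is also fair that baseline PGI-S 5 should be uncommon. Subjects must have shown a 2-point OHSA#1 reduction at Week 4 (Protocol 4.4), and criterion 204 screens for excessive deterioration and expected benefit.

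On the omission from SAP 11.2, the protocol is silent on ceilings, so the rule can be read as filling a gap. Since Protocol 8.1 says that changes to endpoint definitions also go into a protocol amendment, that reading is arguable, and listing the rule is the safer course.

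**Conclusion.** The point holds in a narrow form. As written, SAP 6.4.7 misclassifies one kind of subject on the primary endpoint: baseline PGI-S 5, PGI-S improved at Week 22, OHSA#1 up by at least 1 point. This follows from the text alone and needs no assumption.

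The consequence is probably very small. About 0 to 1 of 154 subjects would be affected if 2% to 10% have baseline PGI-S 5 and the assumed spreads and correlations are near the truth; none of these inputs is in the documents. Equal reclassification of 1% in each arm would change power by about 0.3 percentage points. The case for acting is that the endpoint is primary and the correction is nearly free, not that the result is likely to turn on it.

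**What to change.** Replace the last sentence of SAP 6.4.7 with text to this effect:

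> A subject whose baseline OHSA#1 or PGI-S is already at the scale maximum (for example, PGI-S 5) is a treatment failure if that score is still at its maximum at Week 22 and the other score has worsened by at least 1 point. If both scores were obtained at Week 22 and the score that began at its maximum has improved, the subject is not a treatment failure on this basis. A subject with either score missing at Week 22 remains a treatment failure under the missing-assessment rule.

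The final sentence is needed. Without it, a subject with PGI-S 5 to 4 and no Week 22 OHSA#1 could be read as a non-failure, against the missing-assessment rule.

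Also list the ceiling rule in SAP 11.2 as an addition to the protocol's endpoint definition.

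The cost is a few lines of SAP text and one condition in the derivation code. No new data are needed. The failure count in each arm can only stay the same or fall slightly.
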